Electrical muscle stimulation in the development of acquired weakness in the intensive care unit in adult patients with severe sepsis and septic shock at the Clinic Hospital of the University of Chile: results of a pilot randomized study

17th November 2016

Study protocol

SOFA score and septic focus were recorded, and muscle mass was assessed through ultrasonography (US) at patient's admission. Randomization was applied to assigned the subjects to the intervention group (conventional physical therapy and Electrical muscle stimulation) or to the control group (conventional physical therapy). The intervention was applied until the day when the subject woke up and was able to respond adequately to at least three of five orders of the score of 5 questions test (S5Q): "Look at me", "Open and close your eyes", "Nod your head", "Open your mouth and put out your tongue" and "Raise your eyebrows after I have counted to five". If the subject was able to respond less than three orders it was considered as not cooperative and the assessment was repeated the next day. If subjects fulfilled three or more orders, we proceeded to assess muscle strength measured through the medical research council scale (MRC), maximum inspiratory pressure (MIP), SOFA score and we repeated the measurement of muscle mass through US. Subsequently, the subjects were followed to record days of invasive mechanical ventilation (IMV), presence of weaning failure, days of ICU stay, 28-day mortality, and gait ability at hospital discharge.

Treatment protocol of the control group: conventional physical therapy was used, consisting of early passive mobilization and positioning since subjects' day of ICU admission (levels 0 and 1 of the adaptation of "Start to move" protocol by Gosselink et al.), as long as it met criteria of cardiorespiratory stability according to this protocol.

Treatment protocol of the intervention group: conventional physical therapy was used, but also electrical muscle stimulation (EMS) was applied, starting 48 hours after admission, in bilateral biceps brachii and quadriceps femoris (anterior rectus) muscles. The electrostimulator that we used is a portable model, Ultima Neo®, Pain Management Technologies, Ohio, United States. A set of self-adhesive electrodes was used for each patient. The size of the electrodes was 5x5 cm. for the biceps brachii and 5x9 cm. for the

quadriceps femoris muscles. The parameters used were a frequency of 35 Hz with a pulse width of 250 μ s for the biceps and a frequency of 50 Hz with a pulse width of 400 μ s for the quadriceps. In both, biphasic wave was used, 45 minutes of total work, 5 seconds of contraction and 10 seconds of relaxation and the intensity was adjusted to the point of a visible muscle contraction.

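### No masking of outcome assessors is described, although the arms are recognisable at the bedside and the main strength and muscle outcomes depend on the rater

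*Protocol*

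**What the plan says.** **Arms.** Under the Protocol heading "Study protocol", patients are randomized to physical therapy plus EMS "or to the control group (conventional physical therapy"). No sham is described. In the paragraph on the intervention group, conventional therapy is given "but also electrical muscle stimulation (EMS) was applied, starting 48 hours after admission", through self-adhesive electrodes on both biceps and both quadriceps, and "the intensity was adjusted to the point of a visible muscle contraction".

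**Trigger.** EMS continues until the patient wakes and "was able to respond adequately to at least three of five orders of the score of 5 questions test (S5Q"). A patient who falls short is handled by this rule: "it was considered as not cooperative and the assessment was repeated the next day". The sentence names no assessor.

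**Measurements.** After the trigger, "we proceeded to assess muscle strength measured through the medical research council scale (MRC"), then "maximum inspiratory pressure (MIP), SOFA score and we repeated the measurement of muscle mass through US". The admission ultrasound is described before randomization in the same paragraph.

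**Analysis.** The SAP section "Data analysis" compares muscle strength, ICU-acquired weakness, muscle mass and MIP between arms, alongside ventilation days, ICU days, weaning failure, mortality and walking at discharge. It names Mann-Whitney for between-group data and Fisher's exact test for dichotomous variables. Muscle mass is also the one within-group comparison (Wilcoxon).

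The supplied text does not mention blinding, an independent assessor or a masked image reader. Part of the SAP was not available for this review.

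**The concern.** The outcomes closest to the title's question, acquired weakness and muscle loss, are the ones a rater can move. MRC strength is graded by an examiner. MIP depends on coaching and effort. Ultrasound depends on probe placement and on where the image is measured. If the person doing any of this knows the arm and expects EMS to help, a small systematic difference in scoring looks exactly like a treatment effect. Neither Mann-Whitney nor Fisher's exact test can tell them apart.

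The S5Q trigger adds a second route. It is a judgement that a response was adequate, and it fixes both the end of EMS and the day on which strength, MIP and muscle mass are measured. A judgement that differs by arm near the threshold would change treatment duration and measurement timing, not only a score.

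A pilot signal of this kind may be used to justify or size a later trial, so a spurious one could mislead.

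**Working it through.** The documents give no sample size, SD, effect size or power, so there is no figure of the plan's own to reproduce. The check has two parts.

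**1. Exposure of each measure, from the text**

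| Measure | What the rater contributes | Masking described? |
|---|---|---|
| S5Q trigger | Judging whether a response is adequate; scripted commands, fixed count of three | No |
| MRC strength | Examiner grading | No |
| ICU-acquired weakness | Presence or absence; its definition is not in the supplied text, so dependence on MRC is assumed here | No |
| MIP | A pressure reading, sensitive to coaching | No |
| Repeat ultrasound | Probe placement and image measurement | No |
| Admission ultrasound | The same, but described before randomization | Less exposed |
| 28-day mortality | Essentially none | Not needed |

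The repeat scan enters both the between-group and the within-group comparison of muscle mass.

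**2. What an assumed shift would do to the planned test**

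Inputs:
- Significance level 0.05, from the SAP. Sidedness is not stated; two-sided is assumed.
- Test: Mann-Whitney, from the SAP.
- True effect: none (assumed).
- Constant rater shift δ in favour of EMS: 0.25 or 0.5 SD (assumed).
- n = 10 or 20 per arm (assumed).
- Normally distributed outcome with equal SD (assumed).

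A normal approximation gives the scale. With λ = δ / √(2/n), the chance of significance is Φ(λ − 1.96) + Φ(−λ − 1.96).

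- n = 10: √(2/10) = 0.447, so λ = 0.25/0.447 = 0.56 and 0.5/0.447 = 1.12, giving 8.6% and 20.1%.
- n = 20: √(2/20) = 0.316, so λ = 0.79 and 1.58, giving 12.4% and 35.3%.

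This treats the SD as known and is too generous at these sizes for the test actually planned. Simulating the exact Mann-Whitney test directly (40,000 trials per setting) gives:

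| Shift | 10 per arm | 20 per arm |
|---|---|---|
| 0 | 4.3% | 4.8% |
| 0.25 SD | 7.3% | 11.5% |
| 0.5 SD | 16.1% | 32.0% |

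Smaller simulations agree to within about a percentage point: one of 4,000 trials per setting gave 7.5%, 15.0%, 11.7% and 31.8% for the four shifted settings. That run also covered 50 per arm, where the same two shifts gave about 22% and 68%. A constant rater shift therefore becomes more, not less, likely to reach significance as the trial grows.

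The illustration has limits. S5Q error moves the measurement day rather than adding a constant to a score, so it is not covered, and its direction cannot be derived from the text. The Fisher test of weakness is not covered either. MRC is an ordinal score with ties, which the continuous model ignores.

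**The case against.** The strongest reply is that silence is not evidence. The Protocol is short and part of the SAP was not available, so masked assessment may have been done and not written down. This stands, and it is why the point is worded as masking not being described.

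A reader might infer that the same team treats and assesses. The documents do not say so. The first-person plural around MRC and ultrasound is an authorial form, and the S5Q sentence is passive. That treating staff know the arm does not show that the assessor is one of them.

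A reader might also take all the measures as equally exposed. They are not. The admission scan is described before randomization, S5Q is scripted with a fixed threshold, and MIP is an instrument reading, although coaching matters.

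Two practical objections also stand. Reading coded images offline hides the arm from whoever measures, but not from whoever holds the probe. And a separate bedside assessor depends on staffing that the documents do not describe; since S5Q may be repeated daily, the need could recur over several days.

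The pilot label does not remove the point. It limits how much cost is reasonable, and coding images is within that limit.

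**Conclusion.** The concern holds in a limited form. The arms are recognisable at the bedside. MRC strength, weakness, MIP, the S5Q trigger and the repeat ultrasound depend on judgement, coaching or image reading. No step in the supplied text hides the arm from those who assess them, and the planned tests cannot remove any resulting bias.

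The stronger reading, that assessors knew the arm and that the results are biased, is not supported: the documents establish a vulnerability only. Its size cannot be derived from them. The simulated rates rest wholly on the assumed shift, sample sizes and distribution. They show that a modest shift could matter, not that one exists.

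**What to change.** **Ultrasound (cheap improvement).** Save the admission and awakening images under a study code, and have the same operator measure them in batches without arm or time point. No extra staff are needed. The cost is the effort of coding and the later availability of the values. State plainly that this masks measurement and not image acquisition. If scanning is already complete and images were kept, they can still be re-read this way.

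**Bedside tests (conditional).** Where existing rostering allows it without extra staff, which is an assumption, have S5Q, MRC and MIP done by someone who does not deliver that patient's EMS, with electrodes removed and the stimulator out of sight. Record any unmasking. The cost is scheduling effort, possibly on several days per patient.

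**Otherwise, report it.** If the bedside tests cannot be arranged this way, or were done unmasked, say that these outcomes were assessed unmasked and limit the conclusion accordingly. If assessors were in fact masked, one sentence in the Protocol saying who they were and how the arm was hidden closes the point.

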## Data analysis

Analysis was performed with IBM SPSS Statistics 21.0 software. Non-normality of distribution was checked by employing Kolmogorof-Smirnof test and medium and interquartile ranges were used. Mann-Whitney U Test was used to compare intergroup data (intervention and control), and Fisher's exact test was used for dichotomous variables. Intergroup variables to be compared were muscle strength, presence of ICU acquired weakness, muscle mass, maximum inspiratory pressure, days in mechanical ventilation, days of stay in ICU, weaning failure, mortality and the ability to walk at hospital discharge. Wilcoxon Test was used to compare intragroup data (pre and post intervention). Muscle mass was the intragroup variable to be compared. P values less than 0.05 were considered statistically significant.

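### Follow-up for 28-day mortality, ventilation days and ICU days is placed after the awakening assessment, with no stated time origin or denominator, so it is unclear whether deaths before awakening are counted

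*Protocol*

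**What the plan says.** The protocol gives one sequence.

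- Allocation: "Randomization was applied to assigned the subjects to the intervention group" or to control.
- End of intervention, judged on the S5Q: "The intervention was applied until the day when the subject woke up and was able to respond adequately to at least three of five orders".
- Subjects below three orders: "it was considered as not cooperative and the assessment was repeated the next day".
- Subjects at three or more: "If subjects fulfilled three or more orders, we proceeded to assess muscle strength", together with MIP, SOFA and repeat ultrasound.
- Follow-up: "Subsequently, the subjects were followed to record days of invasive mechanical ventilation (IMV), presence of weaning failure, days of ICU stay, 28-day mortality". Walking at discharge is also recorded.

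The protocol does not say what happens to a subject who dies or remains uncooperative, or when the 28 days begin. The SAP (Data analysis) includes among its between-group comparisons "days in mechanical ventilation, days of stay in ICU, weaning failure, mortality and the ability to walk at hospital discharge". That section states no analysis set, no denominator for mortality and no handling of death in the two duration outcomes.

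**The concern.** MRC and MIP, as sequenced here, wait for a cooperative patient. Vital status, ventilation days and ICU days do not: they can be observed in everyone randomised. Making them wait for awakening is avoidable.

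Awakening occurs after randomisation and could be affected by treatment, so a comparison limited to awakened subjects loses the protection of randomisation. EMS starts 48 hours after admission and stops on awakening, so the period before awakening contains the whole EMS exposure. Mortality is the only listed outcome that directly records death. If deaths before awakening were left out, the comparison would miss those that occur during treatment. In severe sepsis and septic shock, such deaths are plausible.

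Even if nobody is left out, two analysts could take different starting points for the 28 days and different denominators, and so reach different mortality counts.

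**Working it through.** **Text check.** Each step is set against what it provides for a subject who dies before reaching three S5Q orders.

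| Step | Provision for that subject |
|---|---|
| Randomisation | Included |
| Intervention until S5Q criterion | Included until death |
| S5Q below three orders | Repeat next day; no other exit stated |
| MRC, MIP, SOFA, ultrasound | Not reached (conditional on S5Q) |
| Follow-up for mortality, IMV days, ICU days | Comes after the previous step; inclusion not stated |
| SAP comparison of mortality | Denominator not stated |

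The documents contain no sample size, event count or mortality rate, so there is no figure to reproduce. What follows is illustrative: all rates are assumed, and every result requires that only awakened subjects are counted.

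**1. Understated mortality.** Let M be 28-day mortality in all randomised subjects and f the share of those deaths that precede awakening. Mortality among the awakened is M(1 − f)/(1 − Mf).

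| M | f = 25% | f = 50% | f = 75% |
|---|---|---|---|
| 30% | 0.225/0.925 = 24.3% | 0.15/0.85 = 17.6% | 0.075/0.775 = 9.7% |
| 40% | 0.30/0.90 = 33.3% | 0.20/0.80 = 25.0% | 0.10/0.70 = 14.3% |

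With equal f in both arms, a true difference of 40% v 30% (10 points) shrinks to 9.0, 7.4 or 4.6 points.

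**2. Share of deaths missed.** Let p be the proportion dying before awakening, with 10% of awakened subjects dying later. The share missed is p/(p + (1 − p) × 0.10):

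- p = 10%: 0.10/0.19 = 53%
- p = 20%: 0.20/0.28 = 71%
- p = 30%: 0.30/0.37 = 81%

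**3. Unequal early death.** If early deaths differ between arms, the comparison can move either way.

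- *Difference hidden.* Early death 25% control v 40% EMS, later death 10% in both. True mortality is 0.25 + 0.75 × 0.10 = 32.5% v 0.40 + 0.60 × 0.10 = 46.0%. Recorded: 10% v 10%.
- *Sign reversed.* Early death 25% control v 10% EMS, with the extra 15% who reach awakening under EMS dying later at 40%. Later death under EMS is (0.75 × 0.10 + 0.15 × 0.40)/0.90 = 0.135/0.90 = 15%. True mortality is 32.5% v 0.10 + 0.90 × 0.15 = 23.5%. Recorded: 10% v 15%. The reversal depends on the assumed 40%.

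**4. Durations.** Adding early deaths to raw ventilation and ICU days does not settle those comparisons. In a Mann-Whitney test, an early death gives a small number of days and so ranks as a favourable short stay.

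**The case against.** A reader might infer that only awakened subjects were followed and that earlier deaths could not enter the mortality comparison. The documents do not say so. The S5Q condition governs one sentence, the one on strength, MIP, SOFA and ultrasound. The follow-up sentence carries no condition, and its word for the participants is also the one used for everyone randomised. The opening adverb may only give the order of the account. Taken literally as a starting time, it would drop all ventilation and ICU days before awakening, which is a strained reading. The SAP does not restrict mortality to awakened subjects. Part of the SAP was not available for this review and could hold definitions that settle the matter. All the rates above are assumed.

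These points stand, and they rule out a claim that deaths were excluded. They do not supply what is missing. The strained-reading argument bears on when counting starts more than on who is counted, since total days could be tallied for awakened subjects alone. On the inclusive reading, the 28 days still have no origin and the available SAP text still gives no denominator.

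It is also fair that admission is a defensible origin, since the protocol times its measurements and treatments from admission.

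**Conclusion.** The point holds as an ambiguity with real consequences. The protocol puts follow-up for 28-day mortality, ventilation days and ICU days after an assessment that depends on awakening. It gives subjects who die or never reach three orders no path except a repeat S5Q, and it gives no start for the 28 days. The SAP text reviewed gives mortality no denominator. Followed in sequence, this can omit deaths during EMS exposure.

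The stronger inference, that those deaths had no way into the comparison, is not supported, because nothing expressly excludes them.

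The size of any bias cannot be derived from the documents. The figures above show that it could be large and could run in either direction, given the assumed rates and the restrictive reading. They are not evidence that it occurred. The change should be made, because it resolves the ambiguity on either reading.

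**What to change.** **Protocol.** Keep the existing outcome list, including weaning failure and gait at discharge, which the SAP also compares. Add: *All randomised subjects, whether or not they reach the S5Q criterion, are followed for vital status to day 28, IMV days and ICU days, counted from one stated origin (randomisation, or admission if stated) that is the same in both arms.*

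**SAP.** Define mortality as death from any cause within 28 days of that origin, with all randomised subjects in the assigned arm as denominator. Compare ventilation and ICU days so that death does not count as a short stay. For example, give deaths the worst rank in the Mann-Whitney test, or use ventilator-free and ICU-free days to day 28 with death scored 0.

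The documents are written in the past tense, so the same change applies to reporting: state the denominator and the number of deaths before awakening in each arm.

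**Cost.** A few sentences, and a little more record review and analysis work. The data should be in hospital records, though the documents do not say so. The duration outcomes become composites with death, and their interpretation changes accordingly.

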## Data analysis

Analysis was performed with IBM SPSS Statistics 21.0 software. Non-normality of distribution was checked by employing Kolmogorof-Smirnof test and medium and interquartile ranges were used. Mann-Whitney U Test was used to compare intergroup data (intervention and control), and Fisher's exact test was used for dichotomous variables. Intergroup variables to be compared were muscle strength, presence of ICU acquired weakness, muscle mass, maximum inspiratory pressure, days in mechanical ventilation, days of stay in ICU, weaning failure, mortality and the ability to walk at hospital discharge. Wilcoxon Test was used to compare intragroup data (pre and post intervention). Muscle mass was the intragroup variable to be compared. P values less than 0.05 were considered statistically significant.

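### Admission SOFA is recorded but no between-group test uses it: if SOFA predicts the outcomes, precision is given up and a chance severity imbalance stays uncorrected, although the unadjusted tests remain valid

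*SAP*

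**What the plan says.** On admission, the protocol states that "SOFA score and septic focus were recorded", along with ultrasound muscle mass. EMS begins 48 hours after admission, so this SOFA value precedes the treatment that distinguishes the arms. A second SOFA is taken once the patient is awake and cooperative, at the same session as strength: "maximum inspiratory pressure (MIP), SOFA score and we repeated the measurement of muscle mass through US".

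In the SAP, Data analysis, "Mann-Whitney U Test was used to compare intergroup data (intervention and control", and "Fisher's exact test was used for dichotomous variables". The list of comparisons begins "Intergroup variables to be compared were muscle strength, presence of ICU acquired weakness, muscle mass, maximum inspiratory pressure, days in mechanical ventilation" and continues with ICU days, weaning failure, mortality and walking at discharge. SOFA is not on the list, and the section describes no covariate, stratified or regression analysis. The threshold is "P values less than 0.05 were considered statistically significant".

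On allocation, the protocol says "Randomization was applied to assigned the subjects to the intervention group"; the supplied text mentions no stratification by severity. The title describes "results of a pilot randomized study", and the supplied text gives no sample size, effect size or SOFA-outcome correlation. Part of the SAP is not in that text, so the observation is limited to the tests named in Data analysis.

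**The concern.** Organ-failure severity at admission plausibly predicts strength, MIP and length of support. When a baseline measure predicts an outcome, adjusting for it removes part of the unexplained variation, so the same patients give a narrower interval. Adjustment also corrects the estimate for whatever severity difference randomization happened to leave. In a pilot that difference can be appreciable. An unadjusted comparison leaves it in the estimate, where it can mimic or mask an EMS effect. What is at stake is the precision and interpretability of the estimates in the trial actually drawn. The long-run error rate of the test is not in question.

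**Working it through.** The plan states no figure to reproduce, so what follows is an illustration on stated assumptions.

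**Inputs.** From the documents: two randomized arms, Mann-Whitney without covariates, significance at 0.05. Assumed: 1:1 allocation, two-sided testing, 10 to 30 per arm, and a correlation *r* between admission SOFA and outcome of 0 to 0.6.

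**1. Value in patients.** In large samples, adjustment multiplies the variance by 1 − *r*². Estimating the slope costs a further factor (N − 3)/(N − 4) for a normal covariate, with N the total. Relative efficiency is therefore 1 / [(1 − *r*²)(N − 3)/(N − 4)].

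At 10 per arm, N = 20 and the factor is 17/16 = 1.0625:
- *r* = 0.1: 1/(0.99 × 1.0625) = 0.95, a loss of about 5%
- *r* = 0.3: 1/(0.91 × 1.0625) = 1.034, a gain of about 3%
- *r* = 0.6: 1/(0.64 × 1.0625) = 1.47, a gain of about 47%

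Break-even is at *r*² = 1/(N − 3). At 10 per arm this is 1/17, so *r* is about 0.24. At 20 per arm it is 1/37, so *r* is about 0.16. The large-sample formula alone would give 10% at *r* = 0.3 and 56% at *r* = 0.6, which is too generous at 10 per arm.

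**2. Power.** Simulation with bivariate normal data, complete follow-up and a true effect of 0.8 SD. Rank ANCOVA regresses the ranked outcome on arm and ranked SOFA. The rank t-test uses ranks with no covariate. It separates what SOFA contributes from what comes merely from leaving the slightly conservative Mann-Whitney test.

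| Per arm | *r* | Mann-Whitney | Rank t-test, no covariate | Rank ANCOVA |
|---|---|---|---|---|
| 10 | 0 | 35.1% | 38.2% | 36.2% |
| 10 | 0.3 | 35.5% | 38.5% | 39.2% |
| 10 | 0.5 | about 35% | about 38.5% | 44.6% |
| 20 | 0 | 66.8% | as Mann-Whitney | 65.6% |
| 20 | 0.3 | about 67% | as Mann-Whitney | 69.5% |
| 20 | 0.5 | about 67% | as Mann-Whitney | 77.6% |

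The rank t-test ignores SOFA, so its power does not depend on *r*; the value at *r* = 0.5 is carried over from *r* = 0.3. A rerun agreed with these figures within about one point and showed the two covariate-free tests coinciding at 20 per arm.

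Gain attributable to SOFA:
- *r* = 0.3: 39.2 − 38.5 = 0.7 points at 10 per arm; 69.5 − 67 = 2.5 at 20
- *r* = 0.5: 44.6 − 38.5 = 6.1 points at 10 per arm; 77.6 − 67 = 10.6 at 20. With the effect set for nominal 80% power, the figure at 20 per arm is 85.6 − 76.0 = 9.6
- *r* = 0: none, with a slight loss

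**3. Chance imbalance.** The probability that mean SOFA differs by more than 0.5 SD is 2[1 − Φ(0.5/√(2/n))]:
- n = 10: 0.5/0.447 = 1.118, giving 26%
- n = 20: 0.5/0.316 = 1.581, giving 11%
- n = 30: 0.5/0.258 = 1.936, giving 5%

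At *r* = 0.5, a 0.5 SD imbalance moves the outcome difference by 0.5 × 0.5 = 0.25 SD. In null simulations restricted to trials at least that imbalanced, with 20 to 30 per arm, Mann-Whitney rejected in roughly 12% to 16% of runs and rank ANCOVA in about 5%.

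**4. Overall validity.** Over all randomizations with no effect, Mann-Whitney rejected in 4.0% to 4.8% of runs and rank ANCOVA in 4.5% to 5.7%. Both are close to nominal.

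**The case against.** The strongest reply is that the planned test is valid as it stands and that every figure above depends on a correlation the documents do not give. Both statements are true. A reader might infer that ignoring SOFA inflates false positives. It does not, because chance imbalance is already part of the randomized test's error rate. A reader might also infer that power is certainly lost, or that adjustment costs nothing. The documents support neither: at low correlations the gain is nil, and at 10 per arm precision falls slightly.

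The simulation is also kinder than the trial. Strength and MIP are measured only in patients who wake and follow at least three of five orders. This may narrow the range of admission SOFA among those analysed and weaken its correlation with outcome. Early death in the sickest patients can shorten ventilation and ICU days, so SOFA need not relate to those outcomes in one direction. SOFA adjustment repairs neither problem.

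Finally, the SAP is written in the past tense and the title refers to results, so an adjusted analysis added now may be post hoc. That argues for placing it beside the Mann-Whitney test and against replacing that test.

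The objection leaves the central fact untouched: a plausible predictor of outcome is collected before EMS, and none of the named tests uses it.

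**Conclusion.** The point holds in a conditional form. The between-group tests in Data analysis ignore admission SOFA. If SOFA predicts the outcomes, the trial gives up precision and leaves chance severity imbalance uncorrected. On the assumptions of 10 to 20 per arm and 1:1 allocation, the benefit attributable to SOFA runs from nothing at *r* = 0, through about 1 to 3 power points at 0.3, to about 6 to 10 at 0.5. At 10 per arm this is worth about 3% more patients at *r* = 0.3 and 47% at 0.6, with a slight loss below about 0.24. The case is better for strength and MIP than for ventilation and ICU days. The documents do not support calling the Mann-Whitney analysis invalid, or treating the loss of power as established.

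**What to change.** Add to the SAP an analysis adjusted for admission SOFA only, by rank ANCOVA or a proportional-odds model.

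- Apply it to MRC strength and MIP, and secondarily to ventilation and ICU days. For muscle mass, add admission muscle mass as a covariate.
- Report the adjusted effect with a confidence interval beside the Mann-Whitney result. A proportional-odds model gives an odds ratio. A rank-ANCOVA coefficient is in rank units and should be labelled so.
- Do not use the SOFA taken at awakening, because it is measured after randomization and treatment may have affected it. Leave out septic focus, which adds several categories to a small sample.
- Label the analysis post hoc if it is added after results are known.
- State that it does not correct for analysing strength and MIP only in patients who wake and cooperate, or for early death shortening ventilation and ICU days.

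The cost is SAP wording, a few lines of analysis and one degree of freedom per covariate, with a small loss of precision if SOFA turns out not to be prognostic. No new data are needed.

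### Muscle mass is scanned twice, but the between-arm test states no adjustment for the admission scan and does not say whether post values or change are compared; the within-arm tests cannot show a stimulation effect

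*SAP*

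**What the plan says.** The Protocol (Study protocol) records that "muscle mass was assessed through ultrasonography (US) at patient's admission". Once the patient follows at least three of the five S5Q orders, "we repeated the measurement of muscle mass through US". Every patient who reaches that point therefore has a baseline and a follow-up value, the second taken on a day that differs between patients.

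The SAP (Data analysis) assigns between-arm comparisons to the Mann-Whitney test, or to Fisher's exact test for dichotomous variables. Muscle mass is on the between-arm list: "Intergroup variables to be compared were muscle strength, presence of ICU acquired weakness, muscle mass", followed by six further outcomes. No covariate is named, and the quantity to be compared is given only as muscle mass.

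The SAP then adds: "Wilcoxon Test was used to compare intragroup data (pre and post intervention). Muscle mass was the intragroup variable to be compared". The same threshold of p below 0.05 applies to every test. Nothing says how the within-arm results relate to the between-arm comparison.

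**The concern.** The admission scan has a stated role only in a test that ignores randomisation. Three things follow.

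- **Precision.** If the Mann-Whitney test is run on second-scan values, the information in the admission scan is discarded. In a study that its title calls a pilot, that loss can be large.
- **An open choice.** Post values and change are both permitted by the wording, so one outcome has two possible between-arm p-values and nothing fixes which is reported.
- **Interpretation.** A significant fall in the control arm beside a non-significant fall in the stimulation arm looks like a treatment effect but is not a test of one. The SAP does not say that it will be read that way, and does not rule it out.

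**Working it through.** The available text gives no sample size, SD, expected loss or correlation between scans, so there is no stated figure to reproduce. From the documents come the two scans, the Mann-Whitney and Wilcoxon tests and the 0.05 threshold. Assumed here: two-sided testing, equal SD at both scans, correlation rho from 0.3 to 0.9, a true between-arm effect of 0.6 SD, and 10, 15 or 30 patients per arm with both scans.

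**Step 1: variance of the between-arm contrast, relative to post values only.** Post values: 1. Change: 2(1 − rho). ANCOVA: 1 − rho². The ratio of ANCOVA to change is therefore (1 + rho)/2.

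| rho | Post | Change | ANCOVA | ANCOVA/change |
|---|---|---|---|---|
| 0.3 | 1 | 1.40 | 0.91 | 0.65 |
| 0.6 | 1 | 0.80 | 0.64 | 0.80 |
| 0.8 | 1 | 0.40 | 0.36 | 0.90 |
| 0.9 | 1 | 0.20 | 0.19 | 0.95 |

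Post and change are equal at rho = 0.5, since 2(1 − 0.5) = 1. Below that change is worse; above it post is worse. In large samples ANCOVA is never worse than either.

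**Step 2: power, normal data.** Simulation with 10,000 trials per cell; exact Mann-Whitney for post and change, against ANCOVA.

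| Per arm | Test | rho 0.3 | 0.6 | 0.8 | 0.9 |
|---|---|---|---|---|---|
| 10 | Post | 21–22% at every rho | | | |
| 10 | Change | 16% | 27% | 48% | 75% |
| 10 | ANCOVA | 25% | 34% | 55% | 80% |
| 15 | Post | 31.2% | 32.2% | 32.2% | 32.7% |
| 15 | Change | 23.8% | 38.9% | 66.6% | 92.5% |
| 15 | ANCOVA | 36.8% | 49.4% | 73.5% | 94.6% |
| 30 | Post | 60–61% at every rho | | | |
| 30 | Change | 47% | 71% | 94% | 99.8% |
| 30 | ANCOVA | 66% | 81% | 97% | 99.9% |

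At 15 per arm the gain of ANCOVA over post values runs from 36.8 − 31.2 = 5.6 points (rho 0.3) to 94.6 − 32.7 = 61.9 points (rho 0.9). Over change it is 13.0, 10.5, 6.9 and 2.1 points.

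**Step 3: false positives.** With no effect, each of the three tests rejects in 4.2% to 5.3% of trials. If post and change are both tested and either significant result is taken, the rate rises to about 7% to 10%.

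**Step 4: skewed data.** Log-normal, log SD 0.6, 15 per arm, 3,000 trials. The log scale is the true model here, which favours log ANCOVA.

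| rho | Post | Raw change | Raw ANCOVA | Log ANCOVA |
|---|---|---|---|---|
| 0.3 | 33% | 25% | 31% | 37% |
| 0.6 | 33% | 41% | 43% | 51% |
| 0.8 | 31% | 66% | 63% | 73% |
| 0.9 | 33% | 91% | 86% | 94% |

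**Step 5: within-arm tests when the arms are identical.** If each arm's Wilcoxon test has power p to detect the common loss, exactly one is significant with probability 2p(1 − p). This peaks at 2 × 0.5 × 0.5 = 50%. With p simulated at 15 per arm:

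| True loss (SD of change) | 0.2 | 0.3 | 0.5 | 0.6 | 0.8 | 1.0 | 1.2 |
|---|---|---|---|---|---|---|---|
| One arm only significant | 19% | 30% | 49% | 49% | 32% | 11% | 3% |

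Half of these trials show a significant loss in the control arm only. Meanwhile a Mann-Whitney test on change stays at about 4% to 5% (simulated at 10 and 20 per arm).

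**The case against.** The randomised comparison is in the plan, and its test is valid. Nothing in the documents says that the Wilcoxon results will be read as a stimulation effect, and describing muscle loss within an arm is a legitimate aim. Both points stand: the discordance figures apply only if that misreading happens.

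The large gains require post values to be the quantity tested, which the SAP does not say. Against change the gain is modest and shrinks as the correlation rises. This also stands, but because the quantity is unstated, the reader cannot tell which case applies.

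Part of the gain on normal data comes from replacing a rank test with a parametric one. At 15 per arm a t-test on change already beats Mann-Whitney on change by about 3, 4, 5 and 2 points at rho 0.3, 0.6, 0.8 and 0.9. ANCOVA over that t-test gains about 10, 7, 3 and 0 points. So the gain over change that is due to adjustment alone is smaller than Step 2 suggests and disappears at rho 0.9. The gain over post values remains.

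The SAP expects non-normal data, and untransformed ANCOVA on skewed data falls below the change test at rho 0.8 and 0.9 (63% against 66%, and 86% against 91%). That is a reason to settle the scale in advance, not a reason to leave the baseline unused.

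**Conclusion.** The concern holds. It is a matter of precision and specification: neither version of the planned between-arm test is biased. Under the assumed inputs at 15 per arm, leaving out the admission scan costs about 6 to 62 points of power if post values are compared, and about 2 to 13 points if change is compared. Leaving the choice open allows a false-positive rate of about 7% to 10% if the better of the two results is taken. The within-arm tests carry no information on the randomised contrast; read side by side they would mislead in 3% to 49% of trials with identical arms.

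The variance relations in Step 1 need only equal SDs at the two scans. The power and discordance figures rest on assumed arm sizes, effect, loss and correlation, because the available text gives none. The change is worth making because the data are already collected.

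**What to change.** State one between-arm inference for muscle mass: ANCOVA of the second-scan value on arm and admission value, reporting the adjusted difference with a 95% confidence interval. If the measurements are skewed, use the log scale and report an adjusted ratio. Fix the scale before the arms are compared. Rank ANCOVA is an alternative closer to the plan's rank-based approach. Name the muscle and the ultrasound measure that the inference concerns, since the text says only muscle mass.

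Present within-arm changes descriptively, and say that no conclusion about stimulation is drawn from them. If Mann-Whitney is kept as a sensitivity analysis, state whether it uses post values or change.

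The cost is one model in SPSS, one degree of freedom and a check of model assumptions. As the SAP is written in the past tense, it may also mean a re-analysis. The change does not deal with patients who never have a second scan, or with the differing day of that scan; those need their own handling.
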